5.3. Data sources that will be used to collect data about subjects:

Electronic medical records will be reviewed (EPIC) at both institutions (University of Washington and Seattle Children's Hospital). REDCap database will be used to maintain demographic data and collect survey data from parents in intervention and control groups

5.4. Data to be collected, including long-term follow-up data:

**Infant Demographics:** gestational age (weeks), birth weight (g), postnatal age at enrollment and discharge (days)

**Infant characteristics:** Apgar score (5 min), inborn (n), multiparous birth (n), primary and secondary diagnoses (BPD, NEC, PDA, RDS, GI/GU, cardiac, other), IVH (grade), mechanical ventilation at study start (y/n), length of assisted ventilation (days), length of stay (days), any breastfeeding at discharge (y/n)

**Parent Demographics:** age, ethnicity, race, highest level of education, employment status, marital status, other children at home, mode of delivery (vaginal/c-section), experience with yoga before and during pregnancy

**Parent characteristics:** Edinburgh Postnatal Depression Scale scores (located in the infant EPIC chart (UWMC) or the maternal EPIC chart (SCH), or administered by study coordinator at time of enrollment)

**Parent study data:** YIN Introduction Survey, EPDS (if not administered by unit social worker) DASS21, PSS:NICU, PBQ, post-study questionnaire, participation in yoga intervention (tracked on rise website): sessions started (n), duration of participation (min)

**6. Data and Biospecimen Banking**

6.1. Complete list of the data and/or biospecimens to be included in the bank:

- N/A

6.2. Location of data and/or biospecimen storage:

N/A

6.3. List of those with direct access to data and/or biospecimens in the bank:

N/A

6.4. Length of time data and/or biospecimens will be stored in the bank:

N/A

6.5. Procedures for protecting the confidentiality and privacy of the subjects from whom the data and/or biospecimens were collected:

N/A

6.6. How the data and/or biospecimens will be made available for future use:

6.6.1. Who can request data and/or biospecimens from the bank:

N/A

6.6.2. Format in which data and/or biospecimens will be provided:

N/A

6.6.3. Process for investigators to request data and/or biospecimens:

N/A

6.6.4. Restrictions on future use:

N/A

6.6.5. Plan for providing data results from banked data/biospecimens:

N/A

## 7. Sharing of Results

7.1. Plan to share results with subjects/others:

No. Results will be analyzed with the goal of publication in a medical or research journal.

## 8. Study Timelines

8.1. Duration of an individual subject's participation in the study:

6 weeks

8.2. Duration anticipated to enroll all study subjects:

4-6 months

8.3. Estimated date for the investigators to complete this study:

Anticipate completing the study period Jan 2022. Anticipate completion of data analysis May 2022, anticipate manuscripts Sept 2022.

## 9. Study Population

9.1. Inclusion criteria for each subject population (e.g., patients, parents, providers):

- NICU inpatients born <32 weeks gestation at birth and/or <1500g, OR estimated length of stay  $\geq 6$  weeks
- Parents of current NICU inpatients born <32 weeks gestation at birth and/or <1500g OR estimated length of stay  $\geq 6$  weeks
- Parents with any level of experience with yoga (none to regular practitioner)
- Parent age  $\geq 18$  years
- Parent speaks and reads in either English or Spanish

## 9.2. Exclusion criteria for each subject population:

- Expected length of stay of NICU inpatient < 6 weeks
- Parent only speaks or reads in a language other than English or Spanish
- Parent plans to relinquish child
- Child or parents are too unstable as assessed by the Attending Physician

9.2.1. Justification if subjects who use a language other than English or subjects with a parent/legally authorized representative (LAR) who uses a language other than English, will be excluded from the research:

The goal of this pilot study is to generate data to support a parent mindfulness intervention of yoga, breath work, and meditation to reduce stress, depression, and anxiety of parents with infants hospitalized in the NICU. Based on the small sample of parent participants, the inclusion of multiple languages to this study population may confound our research or render appropriate analysis of the data impractical. Further limitations of including a population that uses a language other than English or Spanish include lack of appropriate validated instruments, surveys, or assessments published in other languages to determine parental stress and parent-child bonding for NICU parents.

To improve equity within this project the PI ([name]) is submitting this modification of the current IRB to include Spanish speaking parents. The results of this pilot study will be used to generate a universally accessible parent mindfulness intervention that is inclusive of all ethnicities and languages with the goal to be inclusive of every parent in the NICU regardless of their language of care.

## 9.3. Populations with special considerations, involved in the study:

Children/Teenagers

Risk assessment specific to this vulnerable population and additional safeguards:

Neonates admitted to the NICU at University of Washington and Seattle Children's Hospital are subjects, parents of neonates are participants.

Children who are Wards of the State

Risk assessment specific to this vulnerable population and additional safeguards:

N/A

Adults Unable to Consent 

Risk assessment specific to this vulnerable population and additional safeguards:

N/A

Individuals who use a language other than English

Anticipated language(s) for subjects and their parent(s)/LAR:

All study documents (e.g consent forms, study information sheets, posters), self-report scales, and the study website have been translated into Spanish using the company TransPerfect (official translation certification will be attached in other documents). Given the small sample size of parents participating in this pilot study, the yoga videos will be available on the study website with Spanish subtitles. We are currently working on

obtaining grant funding for the yoga videos to be recorded with Spanish language voice over.

Process to ensure study information is available throughout the research to individuals who use a language other than English:

Study coordinator or her designee will plan to enroll parents using translated study consent forms with in-person interpretation or via video or voice interpreter. Zoom sessions for parents to ask questions of a yoga instructor will also be assisted by a telephone interpreter.

- Neonates of Uncertain Viability or Non-Viable Neonates

Risk assessment specific to this vulnerable population and additional safeguards:

N/A

- Pregnant Women

Additional safeguards:

N/A

- Prisoners

Additional safeguards:

N/A

- Economically or educationally disadvantaged persons

Additional safeguards:

N/A

## 10. Number of Subjects

- 10.1. Total number of subjects to be enrolled locally:

At least 20 parents of NICU inpatients, 20 NICU inpatients

- 10.2. Total number of subjects to be enrolled across all participating sites:

20 parents (and potentially their partners) randomized to control group (10 from UWMC and 10 from SCH)

20 parents (and potentially their partners) randomized to intervention group (10 from UWMC and 10 from SCH)

- 10.3. Number of screened subjects versus the actual number enrolled in the research:

All infants at UWMC and SCH NICU will be screened if born <32-weeks gestation and/or <1500g or LOS estimated >6 weeks

- 10.4. Power analysis:

According to research by Pace et al. (2016) the proportion of parents with low birthweight infants hospitalized in NICUs who endorsed anxiety approached 50%. Smaller studies of parents of very low birthweight infants have shown rates of depression in mothers and fathers ranging from 30-60% (Meyer, EC et al (1994), Davis, L (2003), Mackley, AB, 2010). The study population in Aim 1 (NICU parents) reported a higher level of baseline anxiety and stress (~60%) regarding having an infant in the NICU.

Based on this information, and an anticipated 20-30% decrease in stress and anxiety with yoga practice, we will need a sample size of 16 parents enrolled in each group to see a power of 0.80 at an alpha level of 0.05. Given this information, and the possibility of attrition of study participants, we will plan to enroll 20 parents in control and 20 parents in intervention group for this pilot study.

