- **Meditation (Dhyana)** = guided meditation

The goal of this project is to conduct a pilot study to both allow optimization of engagement for a future definitive study, and to obtain empirical estimates of effect sizes and variability within the target study population.

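### Protocol 10.4: 16 parents per group does not give power 0.80 for a 20-30% decrease from about 60%; two-sided power is about 0.10 to 0.40

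*Protocol*

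**What the plan says.** The sample-size argument is in Protocol section 10.4. It opens with prevalences: for anxiety, "the proportion of parents with low birthweight infants hospitalized in NICUs who endorsed anxiety approached 50" percent; for depression, "rates of depression in mothers and fathers ranging from 30-60" percent; and the parents surveyed in Aim 1 "reported a higher level of baseline anxiety and stress (~60%) regarding having an infant in the NICU". It then adds "an anticipated 20-30% decrease in stress and anxiety with yoga practice" and, explicitly on the strength of those figures, states that "we will need a sample size of 16 parents enrolled in each group to see a power of 0.80" with alpha set at 0.05. Enrolment is set at 20 per group to allow for attrition.

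Section 10.4 names no endpoint, test, sidedness or standard deviation, and does not say whether the decrease is relative or absolute. Section 5.1 says that one goal of the pilot is "to obtain empirical estimates of effect sizes and variability within the target study population".

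**The concern.** The 16 is presented as the result of a calculation from the quoted prevalences and decrease. A comparison of two proportions near 50-60%, differing by 30 points at most, normally needs far more than 16 per group, so the figure called for a check.

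The claim matters because section 1.1 gives the purpose as testing the efficacy of yoga. As written, the protocol tells the IRB and other readers that a true 20-30% effect would be detected four times in five. If the real chance is well under one half, a null result could be mistaken for evidence against yoga. A significant result would tend to overstate the effect, and section 1.1 says these data will be used to plan a multicentre trial.

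**Working it through.** **Inputs from section 10.4.** Alpha 0.05; target power 0.80; 16 per group (20 enrolled); base rate about 60%, with about 50% (anxiety) and 30-60% (depression) as alternatives; decrease 20-30%. **Assumptions.** Two-sided test, with one-sided also tried, because sidedness is not stated; decrease tried as relative and as absolute.

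**What does reproduce.** Going from 16 to 20 corresponds to 20% attrition: 16 / (1 − 0.20) = 20. The 16 itself is the problem.

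**Formulas (two proportions, pooled variance, 1:1).** With p̄ = (p1 + p2)/2, A = √[2p̄(1 − p̄)] and B = √[p1(1 − p1) + p2(1 − p2)]:

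- n per group = (1.960·A + 0.842·B)² / (p1 − p2)²
- power = Φ{ (|p1 − p2|·√n − 1.960·A) / B }

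**Worked case, 60% to 30% (most favourable from 60%).** p̄ = 0.45, A = 0.7036, B = 0.6708.

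- n = (1.960 × 0.7036 + 0.842 × 0.6708)² / 0.30² = 41.97, so 42 per group.
- Power at 16 = Φ[(0.30 × 4 − 1.960 × 0.7036) / 0.6708] = Φ(−0.267) = 0.395.

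**All readings from 60% and 50%, two-sided:**

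| Comparison | Reading | n per group for 0.80 | Power at 16 | Power at 20 |
|---|---|---|---|---|
| 60% v 30% | 30 points | 42 | 0.40 | 0.48 |
| 60% v 40% | 20 points | 97 | 0.20 | 0.24 |
| 60% v 42% | 30% relative | 120 | 0.17 | 0.20 |
| 60% v 48% | 20% relative | 270 | 0.10 | 0.11 |
| 50% v 20% | 30 points | 39 | 0.42 | 0.51 |
| 50% v 30% | 20 points | 93 | 0.21 | 0.25 |
| 50% v 35% | 30% relative | 170 | 0.13 | 0.16 |
| 50% v 40% | 20% relative | 388 | 0.08 | 0.09 |

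**Other choices.**

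- *Fisher's exact test* is less powerful still: 0.27 at 16 per group for 60% v 30%.
- *One-sided test:* power at 16 is at most 0.53 from 60% and 0.56 from 50%; at 20 it is at most 0.61 and 0.64. The smallest one-sided n is 33 from 60% and 31 from 50%.
- *Depression at 30%:* a 20-point fall gives 0.29 two-sided at 16, and a fall to 5% gives 0.46. One-sided with all 20, the fall to 5% reaches 0.68. A 30-point fall would mean a rate of zero and is not counted.

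**What 16 per group can detect.** Solving the power formula for p2 with p1 = 0.60 and power 0.80 gives p2 = 0.139: a fall of 46 points, or 77% relative.

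**Mean-score reading.** For a two-sample t-test (noncentral t, 30 degrees of freedom), 0.80 power at 16 per group needs a standardised difference d = 1.02; at 20 per group, d = 0.91. A 20% fall in the mean equals 1.02 SD only if the SD is 0.20/1.024 = 20% of the mean; a 30% fall, only if it is 0.30/1.024 = 29%. The protocol gives neither mean nor SD. If the SD were 40% of the mean (an assumption), power at 16 would be 0.28 to 0.54 for a 20-30% fall; at 60%, 0.15 to 0.28.

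**Precision.** The 95% confidence interval half-width for a difference in means, in SD units, is t(0.975, 2n − 2)·√(2/n): 0.64 at 20 per group and 0.72 at 16.

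**The case against.** The strongest reply is that a continuous outcome was intended. The instruments in section 5.2 are scored scales: DASS21 subscales are sums of items and PSS:NICU has 26 items. No cut-off or responder definition is given, and the expected effect is worded as a decrease in stress and anxiety rather than in the share of parents affected. The normal-approximation formula for means with d = 1.0 gives n = 2(1.960 + 0.842)² = 15.7, which rounds up to exactly 16 (t-test power at 16 is 0.78). That may be where the figure came from. A one-sided, one-sample test of 60% against 30% also returns 16, but it ignores the control arm.

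It is fair to say that the authors may have worked from d = 1.0, and that the 0.10-0.40 range depends on a binary outcome, a 60% base and a two-sided test. But section 10.4 says its number rests on the prevalences and the 20-30% decrease, and those yield d = 1.0 only with an SD that the protocol does not state. Section 5.1 lists variability among the things the pilot is to estimate. The 40-60% SD range above is an illustration, not a figure from the protocol.

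It can also be said that this is a pilot and that no decision rule hangs on the power. That is a good reason not to claim power at all. It does not support a claim that the inputs contradict, in a protocol whose stated purpose includes testing efficacy. How a null result would be read is a risk, not something the protocol says.

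**Conclusion.** The concern holds. On the protocol's own base rate of about 60% and a decrease of 20-30%, two-sided power at 16 per group is 0.10 to 0.40, not 0.80, so a true effect of that size would be missed at least 60% of the time. The sample needed is 42 to 270 per group. From the 50% base the two-sided range is 0.08 to 0.42.

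These ranges assume a comparison of two independent proportions and cover both the relative and the absolute reading of the decrease. Sidedness is not stated, but a one-sided test with no attrition still reaches only 0.64 from the 50% and 60% bases. On a mean-score reading, 16 is adequate only for a difference of about 1 SD, which nothing in the protocol supports. The statement of power is wrong as written and must be corrected. The planned enrolment of 20 + 20 can stand for a pilot.

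**What to change.** Keep 20 + 20 and rewrite section 10.4:

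- Delete the claim that 16 per group has 0.80 power for a 20-30% decrease.
- State what 16 evaluable parents per group can detect with 0.80 power, two-sided alpha 0.05: a difference of about 1.0 SD, or a fall from 60% to about 14%. With baseline adjustment, and assuming a baseline correlation of 0.5, the first becomes 1.02 × √(1 − 0.25) = about 0.89 SD.
- State that power for the anticipated decrease from 60% is about 0.10 to 0.40.
- Justify the size by precision, using the half-widths of 0.64 SD (20 per group) and 0.72 SD (16 per group). This fits the estimation goal in section 5.1.
- State that a non-significant result will not be taken as evidence of no effect.

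If the investigators did calculate 16 from a mean score, they should instead give the endpoint, test, sidedness, effect scale and SD with their source, and recompute.

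The cost is the rewording of one section, with no extra participants and no change to procedures. The only drawback is a less favourable stated power.

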## 11. Withdrawal of Subjects

11.1. Anticipated circumstances under which subjects will be withdrawn from the research without their consent:

N/A

11.2. Procedures for orderly termination:

N/A

11.3. Procedures that will be followed when subjects withdraw from the research, including partial withdrawal from procedures with continued data collection and withdrawal from data/biospecimen banking:

Parents may withdraw from the study at any time. Data will be retained for analysis even if participant withdraws. Parents will only receive compensation for the portion of the study completed.

## 12. Risks to Subjects

12.1. Reasonably foreseeable risks to subjects (include each study population, each arm, and optional procedures):

**Infants:** risks related to breach of confidentiality due to improper use of personally identifying medical information. To minimize these risks as much as possible, personally identifying information will be stored in the secure manner described in 15.1 below, and only de-identified aggregated data will be used in the analysis.

**Parents:**

**Control group:** Parents will receive usual care available for parental support. There are minimal risks associated with filling out the research questionnaires (depression, social anxiety, parental-child bonding, NICU related stress).

**Intervention group:** Parents in the intervention group will receive usual care for parent support. There are minimal risks associated with filling out the research questionnaires (depression, social anxiety, parental-child bonding, NICU related stress). There is minimal risk of physical injury in the yoga intervention group, as parents will be performing low impact postures designed with the specific physical limitations of post-partum mothers in mind.

Edinburgh Postnatal Depression Scale scores of parents in both control and intervention groups will be accessed from the infant or maternal charts (or administered separately if not administered by social worker or if non-birth parent is participant), thus there are risks related to breach of confidentiality due to improper use of personally identifying medical information.

12.2. Procedures with unforeseeable risks:

N/A

12.3. Procedures with risks to an embryo or fetus should the subject be or become pregnant:

N/A

12.4. Risks to others who are not subjects:

N/A

12.5. Procedures performed to lessen the probability or magnitude of risks:

Risk of breach of confidentiality will be minimized by storing personally identifying information in the secure manner described in 15.1 below, and only de-identified aggregated data will be used in the analysis.

Instructions of how to minimize risks of physical injury will be explained prior to performing physical postures, and during each session. There will be weekly virtual check-in sessions for participants to ask questions in real time to a yoga instructor.

### 13. Potential Benefits to Subjects

13.1. Potential benefits that individual subjects may experience from taking part in the research:

Decrease parental stress, anxiety, and depression in the NICU, helping parents cope with the birth and hospitalization of a preterm infant, improve parent-child bonding.

### 14. Data Analysis/Management

14.1. Data analysis plan, including statistical procedures:

All data will be collected in REDCap spreadsheets and analyzed using STATA 17.0 statistics and data analysis software using appropriate statistical tests. Additional assistance with statistics will be provided by the Institute of Translational Health Sciences (ITHS) Research Services at the UW.

14.2. Quality control procedures for collected data:

Data will be reviewed by study mentors for accuracy

### 15. Confidentiality and Privacy

15.1. Procedures to secure research records, data, and/or biospecimens during storage, use, and transmission:

Record ID, identifying info (name, email address), infant demographics, and participant responses to self-report scales will be stored in a UW REDCap database. Note that any EPDS administered to either birth parent or non-birth parent as part of this study will be linked to the participant by their record ID number. There will be no identifying parent information on any paper forms. Results of EPDS will then be entered by the study coordinator into a secure REDCap form according to participant record ID.

Links to study surveys will be sent to participants directly from REDCap via email and data. Infant medical record numbers and surname will be saved on a password protected file in the Seattle Children's computer server. There will be no patient identifying information associated with the study website.

When using Zoom the following actions will be taken to protect participant confidentiality and privacy: (1) Use the latest version of Zoom available; (2) Make the meeting private; (3) Require a password for meeting entry; (4) Disable private chat. There will be no audio and/or video recording of zoom sessions.

15.2. Steps that will be taken to protect the privacy interests throughout the study:

Yoga sessions are accessed with any smartphone, tablet or PC using the virtual platform, and can be done at the bedside or in the privacy of the parent's lodging or home. Access to the rise website is secure with unique participant username and password. Location of participation is at the discretion of the participant.

15.3. Location where the data and/or biospecimens will be stored:

REDCap database and statistical software. See 15.1 above

15.4. Length of time data and/or biospecimens will be stored:

1 year following the conclusion of the study to allow for analysis and publication

15.5. Individuals with access to data and/or biospecimens:

[name] (Principal Investigator), [name] PhD (faculty Mentor)

15.6. Process for the transmission of data and/or biospecimens outside Seattle Children's:

15.6.1. List of data and/or biospecimens that will be transmitted:

Data will not be transmitted outside of Seattle Children's server except for de-identified data being moved to statistical software package for analysis.

15.6.2. Individual(s) who will transmit data:

[name] (principal investigator)

**16. Provisions to Monitor Data to Ensure the Safety of Subjects**

16.1. Plan to periodically evaluate the data collected regarding both harms and benefits to determine whether subjects remain safe:

Principal Investigator [name] will evaluate self-report data collected in both arms of the study weekly, and report to clinical social worker at specific NICU site regarding any individual parent with concerning symptoms of depression, anxiety or stress that may not have previously been identified.

16.2. Data reviewed to ensure safety of subjects:

Depression, Anxiety, and Stress Scale (DASS21), Parental Stressor Scale: NICU (PSS:NICU), Postpartum Bonding Questionnaire (PBQ).

16.3. Safety information collection procedures:

Individual REDCap surveys will be assigned directly to parents via email. Data will be stored in a longitudinal secure REDCap database.

16.4. Frequency of cumulative data review:

weekly

16.5. Conditions that trigger an immediate suspension of the research:

N/A

